4.4.1.4 RXC004 Pharmacodynamic and Efficacy Data

In pre-clinical pharmacology models, RXC004 demonstrated anti-tumour activity at steady state C_{min} exposures of between ~~CC1~~ and ~~CC1~~ fold IC₅₀, with evidence of improved efficacy at higher doses. The target human exposure to achieve monotherapy efficacy is a C_{min} value of ~~CC1~~-fold IC₅₀.

Pharmacodynamic effects (>50% reduction in AXIN2 expression in skin) were observed in patients who achieved C_{min} exposure of > ~~CC1~~ fold IC₅₀.

As of 30 July 2021, 5/18 evaluable patients in the monotherapy module, with at least 2 scheduled RECIST1.1 scans had achieved durable SD of 10 weeks or longer – 1 patient dosed at 1.0mg QD (RNF43 LoF mCRC), 2 patients dosed at 1.5mg (CCA and RSPO fusion mCRC) and 2 patients dosed at 3mg (CCA and thymus cancer). The CCA patient had a dose reduction to 1.5mg RXC004 after experiencing colitis). Of note all 5 patients who achieved SD had a type of cancer in which RXC004 is most likely to demonstrate clinical benefit based on its mechanism of action. These selected tumour types are CRC or PDAC with a RNF43 LoF mutation or RSPO fusion, or BTC or thymus cancer, both of which are reported to have high Wnt ligand activity (Boulter et al 2015, Loilome et al 2014, Vodicka et al 2020). All patients with RECIST stable disease also achieved C_{min} exposures of ~~CC1~~-fold IC₅₀.

Efficacy data for the combination of RXC004 + nivolumab in Module 2 are not yet available.

4.4.1.5 RXC004 2 mg Monotherapy Dose

Based on all available information, patients who enrol in this study and participate in either Module 1 or in Cohort 1 of Module 2 will receive 2.0 mg RXC004 orally QD.

The 2 mg QD dose was both tolerable and able to consistently deliver C_{min} values of $\text{[CC1]} \text{-fold } IC_{50}$ in all patients, whereas the 1.0 mg and 1.5 mg QD doses did not consistently achieve the target C_{min} values of $\text{[CC1]} \text{-fold } IC_{50}$ in all patients.

The 2 mg dose has been selected for Phase 2 development as the optimal dose to demonstrate an efficacy signal in patients with genetically selected tumours and to allow for potential dose reductions to manage AEs.

4.4.1.6 RXC004 1 mg Monotherapy Dose

Patients who participate in Cohort 2 of Module 2 will receive RXC004 1.0 mg orally QD. The purpose of this cohort is to further characterise the dose-response relationships for activity and safety and to support the optimal dosage(s) for future clinical development.

In the Phase 1 study, the dosing cohorts were small (see Section 4.4.1.1) and patients were not selected for having Wnt ligand-dependent tumours. The median RXC004 exposure was short (approximately 7 weeks); thus, the AEs described in Section 4.4.1.1 were generally observed during the first 2 treatment cycles. Of the observed AEs, only dysgeusia, a known on-target toxicity of Wnt pathway inhibitors, was observed to be dose-related and 4 out of 6 patients in the 2 mg cohort reported dysgeusia within the first 2 treatment cycles. Cohort 2 of Module 2 will explore whether the lower dose of 1 mg has the potential to deliver clinical anti-tumour activity in patients with BTC, a Wnt ligand-dependent tumour, and whether this lower dose has the potential to reduce incidence of treatment related toxicities such as dysgeusia. The 1.5 mg dose was not selected for this purpose because the PK profiles of the 1.5 mg dose and 2 mg dose show considerable overlap.

Initiation of this lower dose cohort will depend on emerging data from the RXC004 2 mg dose cohort. Should the 2 mg dose fail to show any anti-tumour activity in Cohort 1 that warrants further investigation (as per Section 11.9.1), then this lower dose cohort (Cohort 2 of Module 2) will not open unless the SMC consider that the tolerability of the 2 mg QD dose has compromised its ability to show efficacy.

4.4.1.7 RXC004 1.5 mg Dose in Combination with Pembrolizumab

Patients who participate in Module 3 will receive RXC004 1.5 mg orally QD, in combination with pembrolizumab 400 mg IV infusion q6w. Justification for the choice of RXC004 doses and regimens is provided in Section 4.4.1. Justification for the pembrolizumab dose and regimen is provided in Section 12.5.3.

4.5 End of Study Definition

A participant is considered to have completed the study if he/she has completed all phases of the study (including the last visit and the last scheduled assessment shown in the Schedule of Assessments) or withdraws consent, whichever occurs first.

The end of the study is defined as the date of the last visit of the last participant in the study or the last scheduled assessment shown in the Schedule of Assessments for the last participant in the study before the data cut off (DCO).

The Sponsor may terminate this study at any time for reasons that include but are not limited to:

- The discovery of an unexpected, significant, or unacceptable risk to the patients enrolled in the study.
- Inability to complete the trial in a meaningful timeframe due to a lack of recruitment.
- A decision on the part of the Sponsor to modify/suspend or discontinue development of the drug.

5 STUDY POPULATION

The study will recruit male or female patients aged 18 years or older with histologically documented, advanced solid tumours that have progressed after standard of care treatment for advanced (unresectable)/metastatic disease (which varies according to the specific module defined patient population), and have a minimum life expectancy of 12 weeks.

Prospective approval of protocol deviations to recruitment and enrolment criteria, also known as protocol waivers or exemptions, is not permitted.

5.1 Core Inclusion Criteria

Participants are eligible to be included in the study only if all of the following criteria apply:

1. Participant must be ≥ 18 years of age at the time of signing the informed consent.
2. Ability to give written informed consent and capable of understanding the protocol requirements listed in the informed consent form (ICF) and in this protocol. Written informed consent must be obtained prior to performing any protocol-related procedures, including screening evaluations. Participants must be willing and able to comply with the study protocol procedures and restrictions.
3. At least one lesion that is measurable by RECIST 1.1 at baseline (within 6 weeks prior to start of study treatment). The measurable lesion must not be chosen for the mandatory paired biopsies.
4. Mandatory paired biopsies; Patients must have at least one lesion suitable for biopsy at screening (which must not be a target lesion for RECIST 1.1) and be willing to provide mandatory tumour biopsy samples as follows:
 - (i) Baseline* (mandatory and must be performed before study treatment commences, except in exceptional circumstances where biopsy is not technically feasible. All patients without a baseline sample must be approved by Sponsor before starting study treatment as a minimum number of 5 paired biopsies per module are required to achieve the study objectives).
 - (ii) On treatment at C1D15 (+ 7 days). The C1D15 tumour biopsy is also mandatory and should be performed unless the investigator judges that this biopsy is contraindicated (high risk biopsy as defined by ASCO guidelines: Levit et al 2019).
- * Archival biopsy (ideally from the same site that C1D15 biopsy will be taken) that were taken after completion of all prior standard of care treatments will be accepted as a baseline biopsy.
5. Adequate organ and marrow function [Note: for Module 3 the samples must be collected within 10 days prior to the start of study treatment]:

- AST/ALT $\leq 3 \times$ ULN for patients with no Liver Metastasis or AST/ALT $\leq 5 \times$ ULN for patients with Liver Metastasis. [Note: for Module 3, AST/ALT must be $\leq 2.5 \times$ ULN for patients with no Liver Metastasis]
- Total Bilirubin $\leq 1.5 \times$ ULN (with the exception of patients with Gilberts disease [$\leq 3 \times$ ULN])
- Serum Creatinine $\leq 1.5 \times$ ULN
- ANC $\geq 1.5 \times 10^9/L$
- Platelets $> 100 \times 10^9/L$
- Hb $> 9g/dL$ (with or without transfusion support). [Note: for Module 3, this criterion must be met without packed red blood cell transfusion within the prior 2 weeks. Participants can be on stable dose of erythropoietin (\geq approximately 3 months).]
- Calculated CrCL ≥ 60 mL/min as determined by Cockcroft Gault (using actual body weight).

Males:

$$\text{CrCL} = \frac{\text{Weight (kg)} \times (140 - \text{Age})}{72 \times \text{serum creatinine (mg/dL)}}$$

Females:

$$\text{CrCL} = \frac{\text{Weight (kg)} \times (140 - \text{Age})}{72 \times \text{serum creatinine (mg/dL)}} \times 0.85$$

6. Female patients of childbearing potential must have a negative pregnancy test prior to start of dosing. See the Schedules of Assessments for the timings of the required tests. [Note: in Module 3, a woman of child-bearing potential who has a positive urine pregnancy test within 72 hours prior to start of study treatment will be excluded from the study.]
7. Female patients of childbearing potential and male patients with female partners of childbearing potential must agree to use a highly effective method of contraception during the study from the time of treatment initiation, and for at least 5 months after the last dose of study drug. See Section 5.6.1 for details of acceptable methods of contraception

5.2 Module 1 (PDAC) Specific Inclusion Criteria

Participants are eligible to be included in Module 1 if in addition to the Core Inclusion Criteria all of the following criteria apply:

8. Histological documentation of advanced (unresectable)/metastatic (Stage III/IV) pancreatic ductal adenocarcinoma, with documented loss of function tumour mutation in RNF43 from centralised genetic pre-screening activities or from a recognised panel in agreement with sponsor*. Please see Section 5.8 and Appendix F for more details.
*

9. Patients must have received one prior systemic treatment for advanced (unresectable)/metastatic pancreatic ductal adenocarcinoma (Stage III/IV), with clear evidence of radiological disease progression. Patients with advanced disease may also have received prior adjuvant therapy. Patients that have radiologically progressed during or within 6 months of completion of systemic adjuvant chemotherapy may also be allowed (as progression within 6 months of adjuvant treatment may be considered as first-line chemotherapy for metastatic disease).
10. Patients must be enrolled and receive first dose of study treatment within 6 weeks of radiologically confirmed progression. In exceptional circumstances, Sponsor approval for patients to be enrolled within 8 weeks of radiologically confirmed progression may be given (exceptional circumstances may include logistical reasons or patients with indolent, oligometastatic disease).
11. Karnofsky performance status ≥ 70 with no deterioration in the 2 weeks prior to first dose and an estimated life expectancy of greater than 12 weeks (See Appendix G).

5.3 Module 2 and Module 3 (BTC) Specific Inclusion Criteria

Participants are eligible to be included in Module 2 or Module 3 if in addition to the Core Inclusion Criteria all of the following criteria apply:

12. Histological documentation of advanced (unresectable)/metastatic (Stage III/IV) BTC (intrahepatic or extrahepatic cholangiocarcinoma, ampulla of Vater, or gallbladder cancer).
13. Patients must have received one prior systemic treatment for advanced (unresectable)/metastatic Biliary Tract Cancer (BTC), with clear evidence of radiological disease progression (these patients are allowed to have received prior immunotherapy). Patients may also have received prior adjuvant therapy, and additionally, patients that have radiologically progressed during or within 6 months of completion of systemic adjuvant chemotherapy may also be allowed (as progression within 6 months of adjuvant treatment may be considered as first-line chemotherapy for unresectable/metastatic disease).
14. Patients must be enrolled and receive first dose of study treatment within 6 weeks of radiologically confirmed progression. In exceptional circumstances, Sponsor approval

for patients to be enrolled within 7 weeks of radiologically confirmed progression may be given (exceptional circumstances may include logistical reasons or patients with indolent, oligometastatic disease).

15. ECOG status 0 or 1 with no deterioration in the 2 weeks prior to study day 1 and an estimated life expectancy of greater than 12 weeks (See Appendix G).

5.4 Core Exclusion Criteria

Participants are excluded from the study if any of the following criteria apply:

1. Prior therapy with a compound of the same mechanism of action as RXC004.
2. Patients at higher risk of bone fractures, including;
 - a) Patients with Vitamin D [25(OH)D₃] deficiency defined as < 30 nmol/L (< 12 ng/mL). [Note - Patients who fail on this criterion can be given supplementation and be retested within the screening window]
 - b) Patients with a corrected serum calcium level of < 2 mmol/L and serum magnesium level of < 0.60 mmol/L.
 - c) Patients with osteoporosis (as defined by a T-score of < -2.5 at any of the 3 following sites, all of which must be assessed: L/R total hip, L/R femoral neck, lumbar spine (L1-4) by DEXA scan) or history of fragility fractures (any fracture occurring with low-level trauma or as a result of falling < standing height)
 - d) Patients with ongoing or a history of clinically significant hyperparathyroidism, Pagets disease or osteomalacia. Patients with a prior diagnosis of hyperparathyroidism, Pagets disease or osteomalacia, considered by the investigator to have no increased bone fragility risk, may be included.
3. Any known uncontrolled inter-current illness or persistent clinically significant toxicity related to prior anti-cancer treatment (as assessed by the Investigator) which in the investigator's opinion makes it undesirable for the patient to participate in the study.
4. Patients who have any history of an active (requiring treatment) other malignancy (except any in-situ carcinoma, non-melanoma skin carcinoma, and early prostate cancer with a normal PSA) within 2 years of study entry.
5. Patients with known or suspected brain metastases
6. Use of anti-neoplastic agents (including immunotherapy and investigational agents) within 3 weeks prior to the first dose of study treatment, or any residual AEs from prior anti-cancer therapies that have not resolved to Grade ≤ 1 . Use of any investigational drugs within 3 weeks prior to the first dose of study treatment is also

- prohibited. Note: COVID-19 vaccinations that are authorised but not approved should not be considered as investigational agents for the purposes of study eligibility assessment.
7. Patients with a known hypersensitivity to any RXC004 excipients.
 8. Patients with a contra-indication for denosumab treatment including:
 - Known hypersensitivity to denosumab or any of the excipients
 - Severe untreated hypocalcaemia
 - Unhealed lesions from dental or oral surgery
 9. Patients who are pregnant or breast-feeding
 10. Judgment by the investigator that the participant should not participate in the study if the participant is unlikely to comply with study procedures, restrictions and requirements.
 11. Known active HIV, hepatitis B (HBV), or hepatitis C (HCV) infections. Patients with a resolved HBV infection (defined as presence of hepatitis B core antibody [HBcAb] and absence of HBV surface antigen [HBsAg] or negative on polymerase chain reaction [PCR] for HBV DNA) are eligible. Patients positive for HCV antibody are eligible only if PCR is negative for HCV RNA.
 12. Use of any live or live-attenuated vaccines against infectious diseases (e.g., influenza nasal spray, varicella) within 4 weeks (28 days) of initiation of study treatment. Note: Patients that require COVID-19 vaccination within 4 weeks of initiation of study treatment should receive a non-live vaccine (e.g. one based on mRNA or fully inactivated/genetically modified viruses incapable of replication).
 13. Mean resting corrected QTcF >470 ms, obtained from triplicate ECGs performed at screening.

There are no exclusion criteria specific to Modules 1 and 2. Module 3-specific exclusion criteria are listed below.

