5.7 Screen Failures

[figure not shown]
Screen failures are defined as participants who consent to participate in the clinical study but are not subsequently enrolled in the study. A minimal set of screen failure information is required to ensure transparent reporting of screen failure participants to meet the CONSORT publishing requirements and to respond to queries from regulatory authorities. Minimal information includes demography, screen failure details, eligibility criteria, and any SAE.

Individuals who do not meet the calcium and/or vitamin D3 laboratory criteria for participation in this study may be retested after starting calcium/vitamin D3 supplementation. Repeating laboratory tests within the screening period will not be considered as a rescreen.

5.8 Pre-Screening Genetic Testing for Module 1

For Module 1, all enrolled patients' tumours will be required to have a mutation in the RNF43 gene. Eligible patients will be identified by either a central genetics screening approach or local laboratory assessments.

Central Testing - UK

CCI [REDACTED]

Data from central genetic screening will be shared with investigators to aid future treatment decisions.

CCI [REDACTED]

CCI [REDACTED]

CCI [REDACTED]

Local Testing - UK

Patients with predicted loss of function RNF43 mutations from other local testing will also be eligible to enter the study, provided that the assay used for testing has adequate analytical validation for this purpose (i.e. fully CCI [REDACTED] for the purpose of investigating RNF43 mutations; partially CCI [REDACTED] for their analytical performance or having achieved a minimum validation specification of >90% for Analytical Sensitivity / PPA and >95% for Analytical Specificity / NPA for the detection of the aberrations in the genes of interest and performed in an ISO accredited, CLIA or CAP accredited lab). If patients have insufficient CCI [REDACTED] as is often the case for patients with pancreatic cancer, an RNF43 mutation that has been detected in CCI [REDACTED] by a commercial plasma testing panel will be accepted for enrolment, provided the test meets the validation specifications described above. If aberrations are detected by local tests that are not included in the list in Appendix F, these may be included in the study on discussion with the Sponsor, if they are predicted to lead to a loss of function in the RNF43 protein based on pre-determined criteria.

CCI [REDACTED]

CCI [REDACTED]

CCI [REDACTED]

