6.4 Reporting of Concomitant Therapy

Any medication or vaccine (including over-the-counter or prescription medicines, vitamins, and/or herbal supplements) that the participant is receiving at the time of enrolment or receives during the study must be recorded along with:

- Reason for use
- Dates of administration including start and end dates

- Dosage information including dose and frequency

Concomitant medication may be given as medically indicated with the exception of prohibited concomitant medication (Section 5.6.3 and Appendix E).

The timeframe for reporting concomitant therapy is from Screening (within 28 days prior to first dose of study treatment) up to 30 days after last dose of RXC004, and up to 90 days after last dose of pembrolizumab in Module 3. The Medical Monitor should be contacted if there are any questions regarding concomitant or prior therapy.

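### Exclusion 2b joins the calcium and magnesium limits with *and*, so read literally it excludes only patients low in both, and the magnesium limit can only loosen the screen

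*Protocol*

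**What the plan says.** Exclusion 2 in Protocol Section 5.4 opens with "Patients at higher risk of bone fractures, including" and lists four items, (a) to (d). Item (b) reads "Patients with a corrected serum calcium level of < 2 mmol/L and serum magnesium level of < 0.60 mmol/L". No note says whether either value alone is enough.

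Other provisions bear on the same patients:

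- Exclusion 3 leaves room for investigator judgement about uncontrolled illness or "persistent clinically significant toxicity related to prior anti-cancer treatment".
- Exclusion 6 covers "any residual AEs from prior anti-cancer therapies that have not resolved to Grade" 1 or lower.
- Exclusion 8 lists contraindications to denosumab, among them "Severe untreated hypocalcaemia".
- Section 5.7 allows supplementation and retesting for "Individuals who do not meet the calcium and/or vitamin D3 laboratory criteria for participation in this study". It does not name magnesium. It ends: "Repeating laboratory tests within the screening period will not be considered as a rescreen".
- Section 6.4 states: "Concomitant medication may be given as medically indicated with the exception of prohibited concomitant medication". Magnesium can therefore be given.
- Section 2.3.1.2 and the schedules of assessments (Tables 15, 16 and 18) put every patient on calcium 1000-1500 mg daily and vitamin D3 800 IU daily from consent, and on denosumab from Cycle 0 Day 1. The footnotes to Tables 15 and 18 require denosumab before the first RXC004 dose.
- Table 13 includes corrected calcium and magnesium in the safety chemistry.

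**The concern.** A second laboratory limit inside a safety exclusion would normally widen it. Joined by *and*, it narrows it: the magnesium condition has to be met as well before low calcium counts. The result runs against the stated purpose of exclusion 2 and against Section 2.3.1.2, which says patients at high fracture risk are kept out.

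At stake is a consistent screen before mandatory denosumab. A patient with corrected calcium of 1.90 mmol/L and normal magnesium passes 2b and can be stopped only by provisions that state no calcium value. A patient with low magnesium alone meets no magnesium limit at all. Section 5 permits no eligibility waivers, so exact wording matters. SAP Section 4.4.1 classifies eligibility violations as minor or major deviations, and the same patient would be a violation on one reading of 2b and not on the other.

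**Working it through.** The plan gives no figure to reproduce. The check is one of logic.

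**Inputs.** From exclusion 2b, let A be corrected calcium below 2 mmol/L and B be magnesium below 0.60 mmol/L. The lead-in to Section 5.4 excludes a patient who meets any listed criterion. That works between criteria and does not alter the *and* inside 2b.

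**Step 1: rule outcomes.** The values are illustrative, in mmol/L, and chosen to fall on either side of each limit.

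| Corrected Ca | Mg | A and B (as written) | A alone | A or B |
|---|---|---|---|---|
| 1.90 | 0.50 | excluded | excluded | excluded |
| 1.90 | 0.80 | passes 2b | excluded | excluded |
| 2.20 | 0.50 | passes 2b | passes 2b | excluded |
| 2.20 | 0.80 | passes 2b | passes 2b | passes 2b |
| Combinations excluded | | 1 of 4 | 2 of 4 | 3 of 4 |

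**Step 2: effect of the magnesium clause.** The set (A and B) is contained in A. Compared with a calcium limit alone, adding the clause changes only the second row, from excluded to passing. It adds no exclusion.

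**Step 3: size in patients.** Suppose a share *a* of screened patients has low calcium and a share *b* has low magnesium. Then *and* excludes at most min(*a*, *b*), and *or* excludes at least max(*a*, *b*). The documents give neither share, so no patient count follows. The counts of combinations in Step 1 describe the rule and not its frequency.

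**Step 4: is the literal reading strained?** Compare the same list. Items 2c and 2d use *or* where either condition suffices (osteoporosis or past fragility fracture; hyperparathyroidism, Paget's disease or osteomalacia). Exclusion 11 uses *and* where two findings are both required (hepatitis B core antibody present and surface antigen absent). A site that reads 2b as requiring both values is following the protocol's own usage.

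**Step 5: does other text fill the gap?** Exclusion 8 reaches only severe, untreated hypocalcaemia, without a number, and says nothing on magnesium. Exclusions 3 and 6 depend on judgement or on toxicity from prior therapy. The stems of exclusions 2 and 8 are open lists. The bone stopping rules in Table 11 act only after treatment has begun. None of these states a calcium or magnesium value in the protocol text; 2b holds the only ones.

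**Step 6: Section 5.7.** It treats calcium as a criterion a patient can fail, which fits poorly with a rule that has no stand-alone calcium limit. It is not a second defect: its last sentence lets any laboratory test be repeated within screening, and under a literal *and*, correcting calcium alone is enough to clear 2b.

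**The case against.** The strongest reply is that this is an ambiguity and not a proven error. Under an open list of patients at risk, 2b can be read as naming two kinds of excluded patient, and no text states that *or* was meant. That stands: the intent is inferred. It is also a reason to correct the word, since a rule that sites can read two ways needs settling.

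A second reply is that the documents support a calcium limit better than a magnesium-only exclusion. Section 5.7 and the mandatory supplements name only calcium and vitamin D3, and nothing outside 2b ties low magnesium alone to fracture risk or to denosumab. The observation is fair. But 2b does state a magnesium limit, and *or* is the only wording of the two under which that limit excludes anyone. The fix leaves the sponsor free to justify *and* instead.

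Third, Section 5.7 is only moderate evidence, because it remains workable under *and*. That also stands. The main support is the purpose of exclusion 2 and the usage elsewhere in the list.

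Fourth, denosumab contraindications belong to exclusion 8, supplements start at consent, and chemistry is monitored. These reduce the consequence and are why the point is minor. They do not supply a common threshold. Exclusion 6 might imply a number through CTCAE grading, but only for residual toxicity of earlier therapy, and the protocol text states none.

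**Conclusion.** The concern holds. Read literally, 2b excludes one of the four combinations of calcium and magnesium status, against two for a calcium limit alone and three for *or*. The magnesium limit can only release a low-calcium patient from the item. Two groups are missed: low calcium only and low magnesium only. Their size cannot be computed from the documents.

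The conclusion rests on the literal reading of *and*. That *or* was intended is an inference from the purpose of exclusion 2, the usage in 2c, 2d and exclusion 11, and Section 5.7. The point is minor: one word in one eligibility item, with the safety consequence limited by other provisions and no effect on any endpoint, sample size or error rate.

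**What to change.** Reword 2b so that corrected serum calcium below 2 mmol/L *or* serum magnesium below 0.60 mmol/L excludes the patient. If both low values were intended, state that and give the reason.

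Once *or* is adopted, add magnesium in two places in the retest sentence of Section 5.7: to the laboratory criteria a patient may fail, and to the supplements after which retesting is allowed. This is a consequential edit only.

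No new output is needed. Enrolled patients with exactly one baseline value below its limit can be read from the by-patient laboratory listing already planned in SAP Section 4.12.3, which covers corrected calcium and magnesium.

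The cost is one word in 2b and one word in each of two places in Section 5.7. Appendix A 1 requires ethics and regulatory approval for any amendment, so the change should go in with the next one. Using *or* narrows eligibility and may add some retests or screen failures; the documents do not allow a count.
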